6.2 Schedule of Assessments

Table 2 Time and Events Table

Visit	1	2	3	4	5	6	7	8	9	10	11	12	13	14
PROCEDURE	Screening			Rescreening	Baseline								End of Treatment	Follow-up
Gravimetric Timepoint		GSP 1	GSP 2	GSP 3							GSP 4	GSP 5	GSP 6	
Day (allowable window)	Up to 35 days prior to GSP1	Up to 14 days from GSP1 to GSP3			Day 1 (within 7 days of Rescreening)	Day 8 (± 2)	Day 15 (± 2)	Day 22 (± 2)	Day 29 (± 2)	Day 36 (± 2)	Day 41 (±2)	Day 42 (± 2)	Day 43 (± 2)	Day 57 (± 3)
Informed Consent	X													
Medical History, demographics	X			X										
Physical Exam				X										
Vital Signs (blood pressure, heart rate, respiratory rate and temperature)				X	X	X	X	X	X	X			X	X
I/E Criteria	X			X										
Gravimetric Assessments ^{a, b}	X	X	X	X		X	X	X	X	X	X	X	X	X
HDSM-Ax, HDSS	X			X		X	X	X	X	X	X	X	X	X
DLQI				X									X	
Local Tolerability Assessments ^c					X	X	X	X	X	X			X	X
Adverse Events ^c		X	X	X	X	X	X	X	X	X	X	X	X	X
Randomization ^d				X										
Investigational Product ^e (IP) Dispensed / Returned					X ^f			X ^f					X	
IP Weight ^g					X			X					X	
Compliance Evaluation						X	X	X	X	X	X	X	X	
Safety Labs (hematology, chemistry, and urinalysis)	X												X	
UPT (females of childbearing potential only) ^h	X				X				X				X	
Concomitant Medication Review	X	X	X	X	X	X	X	X	X	X	X	X	X	X

- a) Gravimetric assessments for all visits will be conducted from **7:00am-11:00am**.
- b) One 5-minute gravimetric assessment will be conducted for each axilla.
- c) Investigator assessments to be performed after the Subject assessments.
- d) Randomization will take place only after the subject is qualified at the rescreening visit.
- e) Order the investigational product only after the subject is qualified at the rescreening visit and randomized.
- f) Pump 1 of 2 to be dispensed at Baseline (Visit 5). At Day 22 (Visit 8) Pump 2 of 2 to be primed and dispensed to patient. Written instructions for nightly dosing will be given to the subject. Subjects will apply their first dose of gel prior to bedtime the night of their Baseline visit. Instruct the subjects to return Pump 1 of 2 at Day 22 Visit 8 and Pump 2 of 2 at Day 43 (Visit 13, End of Treatment).
- g) Pump container 1 of 2 will be weighed after priming at Baseline prior to dispensing to the subject and upon return at Day 22 (Visit 8). Pump container 2 of 2 will be weighed after priming at Day 22 (Visit 8) prior to dispensing to the subject and upon return at Day 43 (Visit 13, End of Treatment).
- h) FOCBP for this study includes any female 18 years of age or older who has not undergone successful surgical sterilization (hysterectomy, bilateral tubal ligation [at least six months prior to baseline] or bilateral oophorectomy) or is not postmenopausal (defined as amenorrhea greater than 12 consecutive months in women 55 years or older).

6.3 Treatments

6.3.1 *Treatments Administered*

BBI-4000 (sofipirionium bromide) Gel is a clear to slightly translucent colorless gel and is packaged in a white colored, metered pump container. Two pump containers are packaged in a carton with 4 applicators. The total gel volume in each container is 45 mL (~ 40 g). The gross weight of each full container at baseline is approximately 74 to 80 grams. BBI-4000 (sofipirionium bromide) Gel is an anhydrous gel formulation containing the drug substance in a gel base comprising hydroxylpropyl cellulose NF, hexylene glycol NF, isopropyl myristate NF, citric acid anhydrous USP, and alcohol dehydrated USP. Each pump container is sufficient for 21 days of dosing, per protocol instructions. One pump actuation delivers ~ 0.67 mL (~ 0.56 g) of the gel formulation. BBI-4000 vehicle (vehicle) gel will be identical in appearance and constituents to BBI-4000 (sofipirionium bromide) Gel, but will not contain the active ingredient, BBI-4000. Two vehicle pump containers are packaged in a carton with 4 applicators to match the active drug product kits. Subjects will apply the investigational product (BBI-4000 5% or 10% or 15% gel or vehicle gel); once daily at bedtime, to both axilla for 42 consecutive days. One full pump actuation delivers enough gel to apply to one axillae.

6.3.2 *Method of Assigning Subjects to Treatment Groups*

Subjects will be randomized to receive BBI-4000 5%, 10%, or 15% gel, or vehicle gel (vehicle) in a balanced ratio of 1:1:1:1. When subjects qualify for the study (determined by the investigator at the Rescreening Visit), they will be randomized to investigational product groups and will receive a randomization number. The kit carton and treatment plastic pumps have the randomization numbers displayed in their label.

The next eligible subject will be assigned the lowest available randomization number from the treatment kits available at the depot. In this manner, eligible subjects will be randomized to the investigational product sequence in accordance with the randomization schedule. The investigator will document the randomization/kit numbers in the source and on the case report form (CRF). The tear-off portion of the carton label from the outer carton (with blind-break panel) will be removed along the label perforation and placed into the study subject source file. In the event a subject is randomized at the Rescreening Visit but is not dispensed study medication (e.g. deemed ineligible at Baseline due to newly discovered ineligibility, withdraws consent, etc.) the randomization number will not be reassigned; the subject will be considered an early termination and the kit shall be placed in quarantine in the site's inventory.

6.4 Efficacy and Safety Variables

6.4.1 *Efficacy Variables*

The following assessment measures will be conducted to evaluate the efficacy of BBI-4000:

- HDSM-Ax as measured by the subject

- GSP by the investigator
- HDSS as measured by the subject
- DLQI as measured by the subject

6.4.1.1 *Primary Efficacy Variables*

The primary efficacy endpoint is improvement on the HDSM-Ax, defined as:

1. The proportion of subjects achieving at least a 1-point improvement in HDSM-Ax from baseline to end of therapy.
2. Change of HDSM-Ax from baseline to end of therapy as a continuous measure

6.4.1.2 *Secondary Efficacy Variables*

Secondary efficacy endpoints include the following:

1. The proportion of subjects achieving at least a 2-point improvement in HDSM-Ax from baseline to end of therapy.
2. The proportion of subjects achieving at least a 50% reduction in gravimetrically measured sweat production (both axilla combined) from baseline to end of therapy.
3. The absolute change from baseline in gravimetrically measured sweat production to end of therapy.
4. The percent change from baseline in gravimetrically measured sweat production to end of therapy.
5. The ranked change from baseline in gravimetrically measured sweat production to end of therapy.
6. The proportion of subjects achieving at least a 1-point improvement in the HDSM-Ax score and at least 50% reduction in gravimetrically measured sweat production from baseline to end of therapy.
7. The proportion of subjects achieving at least a 2-point improvement in the HDSM-Ax total score and at least 50% reduction in gravimetrically measured sweat production from baseline to end of therapy.
8. The proportion of subjects achieving at least a 2-point improvement in HDSS from baseline to end of therapy.

9. The proportion of subjects achieving at least a 1-point improvement in HDSS from baseline to end of therapy.

6.4.1.3 *Other Efficacy Variables*

Other efficacy endpoints are:

1. The proportion of subjects achieving at least a 1-point improvement in the HDSM-Ax score from baseline to Days 8, 15, 22, 29, 36, 41, 42, 43, and 57.
2. Change in HDSM-Ax from baseline to Days 8, 15, 22, 29, 36, 41, 42, 43, and 57 as a continuous measure
3. The proportion of subjects achieving at least a 2-point improvement in the HDSM-Ax score from baseline to Days 8, 15, 22, 29, 36, 41, 42, 43, and 57.
4. The proportion of subjects achieving at least a 50% reduction in gravimetrically measured sweat production (both axilla combined) from baseline to Days 8, 15, 22, 29, 36, 41, 42, 43, and 57.
5. Percent change from baseline in gravimetrically measured sweat production at Days 8, 15, 22, 29, 36, 41, 42, 43, and 57.
6. Absolute change from baseline in gravimetrically measured sweat production at Days 8, 15, 22, 29, 36, 41, 42, 43, and 57.
7. Ranked change from baseline in gravimetrically measured sweat production at Days 8, 15, 22, 29, 36, 41, 42, 43, and 57.
8. The proportion of subjects achieving at least a 1-point improvement in the HDSM-Ax score and at least 50% reduction in gravimetrically measured sweat production from baseline to Days 8, 15, 22, 29, 36, 41, 42, 43, and 57.
9. The proportion of subjects achieving at least a 2-point improvement in the HDSM-Ax total score and at least 50% reduction in gravimetrically measured sweat production from baseline to Days 8, 15, 22, 29, 36, 41, 42, 43, and 57.
10. The proportion of subjects achieving at least a 2-point improvement in HDSS from baseline to Days 8, 15, 22, 29, 36, 41, 42, 43, and 57.
11. The proportion of subjects achieving at least a 1-point improvement in the HDSS on Days 8, 15, 22, 29, 36, 41, 42, 43, and 57.
12. Change in the modified DLQI from baseline to Day 43 (end of therapy).

6.4.2 *Description of Safety Variables*

The following safety assessment measures will be conducted:

- Adverse events
- Local tolerability assessments including burning, itching, dryness, scaling and erythema
- Vital signs (blood pressure, pulse rate, respiratory rate, and temperature)
- Laboratory tests (hematology, chemistry, and urinalysis) and pregnancy testing in females of child bearing potential.

6.4.2.1 *Adverse Events*

An AE can be any unfavorable and unintended sign (including an abnormal laboratory finding, for example), symptom, or disease temporally associated with the use of a medicinal (investigational) product, whether or not considered related to the medicinal (investigational) product. This definition includes the worsening of a pre-existing condition, the development of investigational product dependency, and suspected investigational product-drug interactions.

6.4.2.2 *Local Tolerability Assessments*

Local tolerability assessments will be evaluated through assessment of selected local signs and symptoms at the drug-application site. Burning, itching, dryness, scaling and erythema will be assessed using standardized 5-point scales (0-Absent to 4-Severe). These assessments are to be performed for both axillae individually. Subject assessments (burning and itching) will be made prior to the Investigator assessments (dryness, scaling and erythema).

Subject Local Tolerability Assessments: Burning and itching for each axilla will be reviewed with the subject and assessed for the previous 24 hours using the standardized scales.

Investigator Local Tolerability Assessments: Dryness, scaling and erythema for each axilla will be assessed by the investigator using the standardized scales.

Local tolerability signs and symptoms that result in the subject's requiring a concomitant therapy, interruption of treatment, or discontinuation from the study, will be reported as an AE.

6.4.2.3 *Vital Signs*

Subjects should be seated for at least 2 minutes prior to measurements. Pulse rate (bpm) will be counted over 60 seconds. Blood pressure (mmHg) will be measured with a sphygmomanometer.

Vital sign measurements will include systolic and diastolic blood pressure, pulse rate, respiratory rate and temperature.

6.4.2.4 Laboratory Parameters

Hematology, clinical chemistry, urinalysis and additional parameters to be tested are listed in Table 3:

Table 3 Laboratory Tests

Hematology		
Platelet Count	RBC Indices:	Automated WBC Differential:
RBC Count	MCV	Neutrophils
WBC Count (absolute)	MCH	Lymphocytes
Reticulocyte Count	MCHC	Monocytes
Hemoglobin		Eosinophils
Hematocrit		Basophils
Clinical Chemistry		
BUN	Chloride	Alkaline phosphatase
Creatinine	AST (SGOT)	Total and direct bilirubin
Sodium	ALT (SGPT)	
Potassium	GGT	
Routine Urinalysis		
Specific gravity		
pH, glucose, protein, blood and ketones by dipstick		
Microscopic examination (if blood or protein is abnormal)		
Other screening tests		
Urine Pregnancy Test (females of childbearing potential* only, using UPT tests provided by the Sponsor.)		
* Females of childbearing potential for this study includes any female 18 years of age or older who has not undergone successful surgical sterilization (hysterectomy, bilateral tubal ligation at least six months prior to baseline or bilateral oophorectomy) or is not postmenopausal (defined as amenorrhea greater than 12 consecutive months in women 55 years or older).		

6.5 Data Quality Assurance

Report summaries will be generated using validated Base SAS® software, version 9.4 or higher, on a PC or server-based platform. Additional validated software may be used to generate analyses, as needed.

All SAS programs that create outputs or supporting analysis datasets will be validated by a second statistical programmer or biostatistician. At a minimum, validation of programs will consist of a review of the program log, review of output or dataset format and structure, and independent confirmatory programming to verify output results or dataset content. Additionally, all outputs will undergo a review by a senior level team member before finalization.

The content of the source data will be reviewed on an ongoing basis by project statistical programmers and statisticians. Data will be checked for missing values, invalid records, and extreme outliers through defensive programming applications, analysis-based edit checks, and

other programmatic testing procedures. All findings will be forwarded to the project data manager for appropriate action and resolution.

7 STATISTICAL METHODS

7.1 General Methodology

Data will be analyzed by Agility Clinical biostatistics personnel. Statistical analyses will be reported with tables, figures, and listings, presented in rich text format, and using recommended ICH numbering. Output specifications for all tables, figures, and listings will be in conformance with guidelines specified by the ICH in Appendix 7 of the *Electronic Common Technical Document Specification* (Apr 2003).

7.1.1 Reporting Conventions

Tables and figures will be summarized by treatment group. Tables summarizing demographics and other baseline characteristics will also include a column for all subjects combined. In general, all data collected and any derived data will be presented in subject data listings, for all enrolled subjects. Listings will be ordered by site, subject number, treatment group, and assessment or event date. The treatment group presented in listings will be based on the planned assignment, unless otherwise noted.

In general, continuous variables will be summarized to indicate the population sample size (N), number of subjects with available data (n), mean, SD, median, minimum, and maximum values. Categorical variables will be summarized by the population size (N), number of subjects with available data (n), number of subjects in each category, and the percentage of subjects in each category. Unless otherwise noted, the denominator to determine the percentage of subjects in each category will be based on the number of subjects with available data. Select ordinal data may be summarized using both descriptive statistics and counts and percentages of subjects in each category, as appropriate.

Non-zero percentages will be rounded to one decimal place. Rounding conventions for presentation of summary statistics will be based on the precision of the variable of summarization, as it is collected in its rawest form (i.e., on the electronic case report form [eCRF] or as provided within an external file) and are outlined as follows:

- The mean and median will be rounded to one more decimal place than the precision of the variable of summarization;
- Measures of variability (e.g., SD, SE) will be rounded to two more decimal places than the precision of the variable of summarization; and
- Minimum and maximum values will be presented using the same precision as the variable of summarization.

Other statistics (e.g., CIs) will be presented using the same general rules outlined above, or assessed for the most appropriate presentation based on the underlying data.

Statistical significance testing will be one-sided as described in Section 7.4.4.1, and performed using $\alpha=0.10$. P-values will be reported for all statistical tests, rounded to four decimal places. P-values less than 0.0001 will be displayed as “<0.0001”; p-values greater than 0.9999 will be displayed as “>0.9999”. Tests of interaction terms, if applicable, will be two-sided and performed using $\alpha=0.10$.

7.1.2 *Standard Calculations*

Where appropriate, the calculated study day of each assessment or event will be presented with the assessment or event date on subject data listings, where study day will be determined as:

- The assessment/event date minus the date of first dose, if the assessment/event date is prior to the date of first dose; and
- The assessment/event date minus the date of first dose, plus one, if the assessment/event date is on or after the date of first dose.

Other variables requiring calculations will be derived using the following formulas:

- **Days:** A duration between two dates expressed in days will be calculated using the following conventions:
 - Later date – earlier date + 1, if the earlier date is on or after the date of first dose of study drug; or
 - Later date – earlier date, if the earlier date is prior to the date of first dose of study drug.
- **Change from Baseline:** Change from baseline will be calculated as the post-baseline value minus the baseline value;
- **Percentage Change from Baseline:** Percentage change from baseline will be calculated as the change from baseline divided by the baseline value, multiplied by 100.
- **Rank Transformation:** All raw data will be ranked together within time point without regard to treatment group, from smallest value to highest value. The smallest observation will be assigned the rank of 1, the second smallest the rank of 2, and so on. Average ranks will be used for tied observations.

Unless otherwise noted, values reported as greater than or less than some quantifiable limit (e.g., “< 1.0”) will be summarized with the sign suppressed in summary tables and figures, using the numeric value reported. Data will display on subject listings to include the sign.

7.2 Analysis Populations

The analysis populations are defined as follows:

- **Safety Population:** Includes all subjects randomized in the study who received study drug at least once. Subjects will be included in the treatment group based on the lowest dose of active treatment they actually received (even if not the treatment group to which they were randomized). Thus, a subject randomized to 15% BBI-4000 but who actually received 10% and 5% would be included in the 5% BBI-4000 group. A subject randomized to vehicle but who actually received 5% and 10% would be included in the 5% BBI-4000 group.
- **Modified Intent-to-Treat (mITT) Population:** Includes all subjects who were randomized and dispensed study drug. Subjects will be included in the treatment group to which they were randomized, regardless of the treatment received.
- **Per-Protocol (PP) Population:** Includes all Safety Population subjects who meet the following criteria:
 1. Meets the inclusion/exclusion criteria
 2. Has not taken or applied any interfering concomitant medications.
 3. Completed the following visits:
 - Visit 2 GSP 1, and the required GSP data collection
 - Visit 3 GSP 2, and the required GSP data collection
 - Visit 4 GSP 3, and the required GSP data collection
 - Visit 11 GSP 4, and the required GSP data collection
 - Visit 12 GSP 5, and the required GSP data collection
 - Visit 13 GSP 6, and the required GSP data collection

Subjects will be included in the treatment group based on the treatment actually received, as described above.

Data summaries to be presented on both the Safety Population and the mITT Population will only be produced on both analysis sets if there is a difference in the population groups (e.g., at least one subject receives a different treatment than they were originally assigned or some subjects never received any protocol treatment).

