7.3 Study Subjects

7.3.1 *Disposition of Subjects*

Subject disposition will be summarized for all randomized subjects by treatment group and over all subjects combined. Summaries will include the number and percentage of subjects in each analysis population, completing the study, and discontinuing the study early by the primary reason for discontinuation. Subject disposition will also be summarized separately for each study center.

7.3.2 *Protocol Deviations*

Major protocol violations will be summarized by treatment group and over all subjects combined for the Safety Population. Major protocol violations may include, but will not be limited to the following:

- Violation of eligibility criteria;
- Randomization error;
- Non-compliance with study drug dosing;
- On-study administration of a prohibited medication;
- Unauthorized changes to protocol procedure that could potentially affect subject safety or are a flagrant deviation of protocol defined procedures

All major protocol violations will be determined and appropriately categorized prior to database lock and prior to breaking the blind of the treatment group assignments. The number and percentage of subjects with any major protocol violations as well as the number and percentage of subjects with violations within each category will be presented. A per subject listing will be provided for all protocol violations. All protocol violations will be determined and appropriately categorized prior to database lock.

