7.7 Changes in the Conduct of the Study or Planned Analyses

Analysis of change in DLQI score between baseline and Day 57 removed as this data is not collected.

An explanation of how subjects receiving multiple doses will be assigned to dosage groups in the Safety Population was added.

ITT population was changed to mITT population.

The Per Protocol population definition was changed to a subset of the Safety population, as subjects must receive one dose of study drug.

An Imputed End of Therapy time point added to primary and secondary outcomes as a sensitivity analysis.

GSP data to be analyzed separately with baseline/EOT mean value and baseline/EOT median value.

MMRM sensitivity analysis expanded to include GSP continuous (raw and ranked) data, and a logit-linked, generalized MMRM analysis of HDSM-Ax, GSP, and HDSM-Ax+GSP binary outcomes.

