APPENDIX B: TABLE LAYOUTS

Brickell Biotech, Inc.
BBI-4000-CL-203

Database Date/Analysis: DDMMYYYY/Draft
Page x of y

Table 14.1.1.1
Subject Disposition
All Randomized Subjects

	Vehicle (N=)	BBI-4000 5% (N=)	BBI-4000 10% (N=)	BBI-4000 15% (N=)	Total (N=)
All Randomized	n (x.x%)	n (x.x%)	n (x.x%)	n (x.x%)	n (x.x%)
Study Medication not Dispensed	n (x.x%)	n (x.x%)	n (x.x%)	n (x.x%)	n (x.x%)
Safety Population ^[1]	n (x.x%)	n (x.x%)	n (x.x%)	n (x.x%)	n (x.x%)
mITT Population ^[2]	n (x.x%)	n (x.x%)	n (x.x%)	n (x.x%)	n (x.x%)
PP Population ^[3]	n (x.x%)	n (x.x%)	n (x.x%)	n (x.x%)	n (x.x%)
Completed Study ^[4]					
Yes	n (x.x%)	n (x.x%)	n (x.x%)	n (x.x%)	n (x.x%)
No	n (x.x%)	n (x.x%)	n (x.x%)	n (x.x%)	n (x.x%)
Primary reason for Discontinuation					
Adverse Event	n (x.x%)	n (x.x%)	n (x.x%)	n (x.x%)	n (x.x%)
Withdrawal by Subject	n (x.x%)	n (x.x%)	n (x.x%)	n (x.x%)	n (x.x%)
Physician Decision	n (x.x%)	n (x.x%)	n (x.x%)	n (x.x%)	n (x.x%)
Protocol Violation	n (x.x%)	n (x.x%)	n (x.x%)	n (x.x%)	n (x.x%)
Lost to Follow-Up	n (x.x%)	n (x.x%)	n (x.x%)	n (x.x%)	n (x.x%)
Death	n (x.x%)	n (x.x%)	n (x.x%)	n (x.x%)	n (x.x%)
Pregnancy	n (x.x%)	n (x.x%)	n (x.x%)	n (x.x%)	n (x.x%)
Worsening Condition	n (x.x%)	n (x.x%)	n (x.x%)	n (x.x%)	n (x.x%)
Lack of Efficacy	n (x.x%)	n (x.x%)	n (x.x%)	n (x.x%)	n (x.x%)
Study Terminated by Sponsor	n (x.x%)	n (x.x%)	n (x.x%)	n (x.x%)	n (x.x%)
Other	n (x.x%)	n (x.x%)	n (x.x%)	n (x.x%)	n (x.x%)

Abbreviations: GSP, gravimetrically measured sweat production; mITT, Intent-to-Treat; PP, Per-Protocol

^[1] Safety Population includes all subjects randomized in the study who received study drug at least once. Treatment group assignment is based on the treatment actually received.

^[2] mITT Population includes all subjects who were randomized and dispensed study drug. Treatment group assignment is based on the planned treatment assignment.

^[3] PP Population includes all Safety subjects who meet all inclusion/exclusion criteria, have not taken/applied any interfering concomitant medications, and have full data collected for all GSP visits.

^[4] Defined as a disposition term of "Normal Study Completion".

Reference: Listing #(s)

Path\filename.sas ddmmmyyyy hh:mm

Table 14.1.1.2
Subject Disposition by Study Center
All Randomized Subjects

		Vehicle (N=)	BBI-4000 5% (N=)	BBI-4000 10% (N=)	BBI-4000 15% (N=)	Total (N=)
Site 1	All Randomized	n (x.x%)	n (x.x%)	n (x.x%)	n (x.x%)	n (x.x%)

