HDSM-Ax and GSP Parameters	Time Point	Vehicle	BBI-4000 5%	
		(N=)	(N=)	P-value ^[1]
		n (%)	n (%)	
HDSM-Ax reduction from Baseline ^[2] ≥ 1 and GSP reduction from Baseline ^[2] ≥ 50%	Day 8	n (x.x%)	n (x.x%)	x.xxxx
	Day 15	n (x.x%)	n (x.x%)	x.xxxx
	Day 22	n (x.x%)	n (x.x%)	x.xxxx
			
	End of Therapy ^[3]	n (x.x%)	n (x.x%)	x.xxxx
	MMRM treatment p-value ^[4]			x.xxxx
	MMRM treatment*visit p-value ^[5]			x.xxxx
HDSM-Ax reduction from Baseline ^[2] ≥ 2 and GSP reduction from Baseline ^[2] ≥ 50%				
....				

Abbreviations: GSP, gravimetrically measured sweat production; HDSM-Ax, Hyperhidrosis Disease Severity Measure-Axillary; mITT, Intent-to-Treat; MMRM, mixed model for repeated measures

Note: Responder is defined as a subject who achieved the reduction in HDSM-Ax score specified in the HDSM-Ax Parameter column, between Baseline and End of Therapy. Subjects without a defined improvement in score are considered non-responders.

^[1] P-values comparing active treatment to vehicle are based on a binary logistic regression model where treatment and baseline HDSM-Ax Score are predictors.

^[2] HDSM-Ax baseline is defined as the average of any available Visit 1 (Screening) and Visit 4 (Rescreening) values; GSP baseline is defined as the median of any available GSP measurements from Visit 2, Visit 3, and Visit 4.

^[3] HDSM-Ax End of Therapy is defined as the average any available Day 41, Day 42, and Day 43 values; GSP End of Therapy is defined as the median of any available GSP measurements from Day 41, Day 42, and Day 43.

^[4] P-values comparing active dose to vehicle are based on an MMRM with subject as a random effect, treatment, protocol-specified visit, baseline, and baseline*visit interaction as fixed effects.

^[5] P-value is for the collective treatment*visit interactions based on an MMRM with subject as a random effect, and treatment, protocol-specified visit, treatment*visit interaction, baseline, and baseline*visit interactions as fixed effects.

Reference: Listing #(s)

Path\filename.sas dddmmyyy hh:mm

Programming Notes: Continue for Days 29, 36, 41, 42, 43, 57, HDSM-Ax ≥ 2, and remaining BBI-4000 dose groups (10%, 15%); Repeat as Table 14.2.2.2 HDSM-Ax and GSP Responder MMRM (PP Population). MMRM = generalized linear mixed model for repeated measures, with logit linkage. For MMRM analyses, use data on Days 8, 15, 22, 29, 36 and End of Therapy.

Table 14.2.3.1
GSP Summary of First and Last Visits
mITT Population

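### The Per-Protocol set has no adherence criterion beyond one dose, so the PP tables for HDSM-Ax screen for attendance and not for dosing

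*SAP*

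**What the plan says.** SAP 7.2 says of the PP set that it "Includes all Safety Population subjects who meet the following criteria", and then sets three conditions: "Meets the inclusion/exclusion criteria"; "Has not taken or applied any interfering concomitant medications"; and completion of Visits 2, 3, 4, 11, 12 and 13 with GSP data at each, the last being "Visit 13 GSP 6, and the required GSP data collection". The footnote to Table 14.1.1.1 restates the third as subjects who "have full data collected for all GSP visits". Protocol 10.1 has the same three conditions. The only exposure requirement comes through Safety Population membership; SAP 7.7 explains the subset "as subjects must receive one dose of study drug".

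Elsewhere the SAP does deal with adherence:
- Section 7.3.2 gives examples of major protocol violations, to be determined before the blind is broken. One is "Non-compliance with study drug dosing". No threshold is stated.
- Section 7.4.3 defines percent compliance, with expected doses counted from first to last dose, and summarises it in the Safety and PP sets.
- Table 14.3.5.2 (Safety Population) displays subjects below and at or above 80%.

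None of these feeds into the PP definition. PP tables are planned for the primary endpoint: 14.2.1.4, 14.2.1.6 and 14.2.1.8.

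**The concern.** Two of the violation examples in SAP 7.3.2, eligibility and prohibited medication, have a counterpart among the PP criteria. Dosing does not. The PP tables for HDSM-Ax can therefore include subjects who applied little of the gel. They also exclude some who applied all of it and have every HDSM-Ax value, because of a GSP reading that HDSM-Ax does not use. If the PP and mITT results agree or differ, the reader cannot tell what that says about subjects who followed the regimen. At stake is how a supportive analysis is interpreted, not the trial's primary test.

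**Working it through.** **The plan's own figures.** The documents state no size or power for PP. The stated power (SAP 7.6) is for 50 evaluable subjects per arm at one-sided 0.10.
- Binary, 75% versus 50%, with continuity correction: null SE = √(2 × 0.625 × 0.375/50) = 0.0968; alternative SE = √(0.75 × 0.25/50 + 0.5 × 0.5/50) = 0.0935; power = Φ[(0.25 − 0.02 − 1.2816 × 0.0968)/0.0935] = 0.871, against 0.87 stated.
- Continuous: Φ[0.18/(0.36 × √(2/50)) − 1.2816] = Φ(1.218) = 0.888, against 0.89 stated.

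**Who stays in PP.** Planned doses are 42 nights × 2 axillae = 84. Both subjects below are taken to be eligible, free of interfering medication and present at all six GSP visits.

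| Subject | Doses applied | Share of 84 planned | SAP 7.4.3 compliance | In PP? |
|---|---|---|---|---|
| Misses 21 nights between first and last dose | 42 | 50% | 42/84 = 50% | Yes |
| Stops gel after 14 days, keeps attending | 28 | 33% | 28/28 = 100% | Yes |

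The SAP provides for the second case: Listing 16.2.1 records completion of treatment and completion of study separately.

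**Who is dropped.** HDSM-Ax is collected at Visits 1, 4 and 6 to 14, not at Visits 2 or 3 (Time and Events Table). Its baseline is the average of any available Visit 1 and Visit 4 values, and end of therapy is the average of any available Day 41 to 43 values (Table 14.2.1.3 footnotes). A subject with all of these but no Visit 2 GSP fails PP. Even the GSP endpoint does not need all three baseline readings: "GSP baseline is defined as the median of any available GSP measurements from Visit 2, Visit 3, and Visit 4".

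Let m be the share missing GSP at each of Visits 2 and 3 (assumed). The loss unrelated to HDSM-Ax is 1 − (1 − m)² under independence:
- m = 2%: 1 − 0.98² = 0.040
- m = 3%: 1 − 0.97² = 0.059
- m = 5%: 1 − 0.95² = 0.098

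If the same subjects miss both visits, the loss falls towards m. Whatever the dependence, it cannot exceed 2m, which is 4%, 6% or 10%.

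**Possible dilution (illustration only).** Suppose a fraction f of active-arm PP subjects did not use the gel and responded like vehicle. The 25-point difference becomes 25 × (1 − f). For f = 10%, 20% and 30% it is 22.5, 20.0 and 17.5 points. Power by the formula above, at 50 per arm, is then 0.80, 0.71 and 0.62. The documents give no value for f.

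**The case against.** Much can be said for the plan as written.

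- **PP does screen on retention.** Protocol 7.4 asks early discontinuers only for the Visit 13 evaluations, so they normally fail the Visit 11 and 12 requirement. It would be wrong to infer that PP removes no under-dosed subjects. What remains is the non-adherent subject who keeps attending, and the documents do not say how many there will be.
- **Most of the six-visit rule overlaps with HDSM-Ax.** A reader might take the whole loss, 1 − 0.98⁶ = 11.4%, 1 − 0.97⁶ = 16.7% or 1 − 0.95⁶ = 26.5%, as unrelated to the primary endpoint. That is not supported. HDSM-Ax is also collected at Visits 4, 11, 12 and 13, so missing one of those visits loses HDSM-Ax data too, and Visit 4 is where eligibility is confirmed and randomization requested. A GSP reading lost at an attended visit would add something, but the documents give no basis for its frequency.
- **The violation list is illustrative.** SAP 7.3.2 is open-ended and sets no cut, so it does not firmly class any given subject as a major dosing violator.
- **Not every missing reading excludes.** SAP 7.4.5 imputes a missing single axilla, and Table 14.2.3.4 counts such gaps within PP, so those subjects may stay.
- **PP is supportive.** The primary analysis is on mITT, and nothing says that PP estimates the effect under full adherence. Compliance within PP is summarised and exclusions are listed with reasons, so a reader can see part of the problem.
- **One common PP set has merit.** It keeps HDSM-Ax, GSP and the composite responder endpoints on the same subjects.

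All of these stand and limit the size of the point. None supplies the missing dosing criterion.

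**Conclusion.** The point holds as a minor, inexpensive improvement. Among subjects who attend Visits 11 to 13, PP does not distinguish those who used the gel from those who did not. That follows directly from the text of both documents and needs no assumption. The number of subjects affected is unknown.

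The separate loss of adherent subjects with complete HDSM-Ax data, through Visits 2 and 3, is about 4%, 6% or 10% at assumed missed-visit rates of 2%, 3% or 5%, and less if misses cluster within subjects. The dilution figures likewise depend on an assumed share of non-users.

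A reader might infer that the primary result or its false-positive rate is at risk. The documents do not support that: the mITT analysis, the gatekeeping and the stated power do not depend on PP.

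**What to change.** Add a fourth PP criterion to SAP 7.2, for example: *no major dosing violation, defined before unblinding as fewer than a pre-specified share of the planned doses (42 nights × 2 axillae = 84)*. The 80% cut already displayed in Table 14.3.5.2 is a natural choice; on 84 doses it keeps subjects with at least 68 (68/84 = 81%; 67/84 = 79.8%).

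Do not use the compliance percentage of SAP 7.4.3 for this. It scores the subject who stops after 14 days as 100% compliant and would keep the case the rule is meant to exclude. The visit window does no harm: if Visit 13 falls on Day 41, with the last application the night before, 40 nights × 2 = 80 doses, or 95% of 84.

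Record the departure from Protocol 10.1 in SAP 7.7.

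Optionally, for the HDSM-Ax and HDSS PP tables, do not exclude a subject solely for a missed GSP1 or GSP2 when that endpoint's baseline and end-of-therapy values are evaluable.

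The cost is SAP wording and a derivation from dosing data already collected, with major violations already due to be settled blind. The adherence rule makes the PP set slightly smaller. It also selects on post-randomization behaviour, so PP stays supportive. The optional change would make PP sets differ slightly by endpoint.
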